9.4 Covariates and Subgroups

Demographic and baseline values will be collected and analyzed on all participants. Data on age, gender, race/ethnicity, medical diagnoses, sleep prescriptions, sleep supplements, alcohol and cannabis use, smartphone operating system (Android or iOS), and use of personal health tracker

(e.g. Apple Watch, Fitbit) will all be collected and included in univariate, bivariate, and multivariate analyses. Subgroup analyses will be conducted to examine differences in outcome by all covariates available.

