3.2 Eligibility

Participants must meet all the following criteria on screening examination to be eligible to participate in the study:

Inclusion

1. Age \geq 18 years old
2. Has self-reported sleep disturbance
3. Insomnia Severity Index (ISI) score of \geq 15 at screening
4. Interested in understanding more about the quality of their sleep and chose to use the Sip2Sleep product for sleep
5. Willingness to do a minimum of 1 week wash out of current OTC or other products for sleep (e.g. melatonin, anticholinergics)
6. Willingness to do a minimum of 1 week wash out of any cannabis products
7. Able to receive shipment of the product at an address within the United States
8. If taking prescription hypnotics (e.g. zolpidem, zaleplon, benzodiazepines) or other class of medication for sleep, must be on a stable dose for at least 4 weeks.
9. Able to read and understand English
10. Able to use a personal smartphone
11. Has and is able to use a personal health tracking wearable device (e.g., Apple Watch, Fitbit Smartwatch, Oura Ring, etc.)
12. Able to understand and provide informed consent
13. Able to complete study assessments over 5 weeks

Exclusion

1. Research participants who have no computer, smartphone, and internet access and/or do not use a computer or smartphone
2. Concomitant Therapies:
 - a. Participants taking daily prescription medication for sleep (for example, prescription hypnotics like zolpidem, zaleplon, benzodiazepines) not on a stable dose for at least 4 weeks
 - b. Participants receiving Cognitive Behavioral Therapy for Insomnia (CBTi)

- c. Participants receiving any investigational therapies or treatments
3. Other Illnesses or Conditions: Participants who have the following co-morbidities are excluded:
- a. Confirmed diagnoses of the following sleep disorders: Narcolepsy, Restless Leg Syndrome, Circadian Rhythm Disorders
 - b. Confirmed diagnosis of Sleep Apnea that is untreated or not well controlled
 - c. Current or prior psychotic disorder
 - d. Current or prior Substance Abuse Disorder
 - e. Current or prior cardiac dysrhythmias (for example, atrial fibrillation, supraventricular tachycardia)
 - f. Currently pregnant, planning to become pregnant in the next 1 month, or breastfeeding
 - g. Allergies or adverse reactions (for example, anxiety) to Montmorency tart cherry extract and/or Venetron®

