9.6 Statistical Analysis Plan

The primary objective of this study is to determine the impact of Sip2Sleep® use on symptoms of sleep disturbance, as measured by the change in sleep quality VAS scores from 47 participants. Univariate statistics will be generated to describe the distribution of patient characteristics and outcome data. Continuous variables will be described using means, standard deviations, minimums and maximums while categorical variables will be described using counts and percentages. Sleep quality VAS scores will be compared from baseline pre-treatment; and at end of study (post-treatment) of the same individuals. We will enroll up to 80 participants to achieve at least 90% power to detect a mean change in sleep quality VAS scores of 1 points (SD=2) from baseline with a type I error of 0.05 (two-sided) assuming a paired means, dependent Wilcoxon Signed-Rank test. We are testing the null hypothesis that there is no difference between pre-treatment and post-treatment mean sleep quality VAS scores within study participants. Summary statistics will be generated, and paired differences between pre-treatment and post-treatment sleep quality VAS scores will be reported, along with 95% confidence intervals.

Additionally, parametric linear mixed models will be employed to simultaneously account for correlated observations and adjust for confounding variables (Proc Mixed, SAS). Several covariance structures, including compound symmetry and unstructured, will be evaluated by comparing AIC and BIC to identify optimal model fit. Random slope and intercept will also be considered in a similar manner. Patient characteristics (i.e. age and sex) will be included in adjusted models a priori for confounding control. Directed acyclic graphs will be employed to select other potential confounding variables and identify biases during the model fitting process. Large differences will be further examined and may help identify where further calibration of estimation models are needed.

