Stratified and interaction analyses will be employed to detect between-subgroup differences in outcomes. Specifically, we will test the difference in sleep quality VAS score change between sexes and those who reported moderate-to-severe insomnia disorder on the ISI (i.e. ISI score > 14) and those who did not (i.e. ISI score ≤ 14). Testing of these differences will be conducted by including 2-way product terms between the exposure and covariate of interest in linear mixed modeling. A significant interaction will be defined by an interaction coefficient with a p-value < 0.05.

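### Subgroups are planned on every available covariate with an unadjusted p < 0.05 interaction rule, no multiplicity control and no exploratory label, and the plan does not say how far that rule reaches

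*Combined protocol and SAP*

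**What the plan says.** Section 9.4 gives the covariate list: "Data on age, gender, race/ethnicity, medical diagnoses, sleep prescriptions, sleep supplements, alcohol and cannabis use, smartphone operating system (Android or iOS", followed by use of a personal health tracker. These "will all be collected and included in univariate, bivariate, and multivariate analyses", and the section then commits to subgroup work without limit: "Subgroup analyses will be conducted to examine differences in outcome by all covariates available". It sets no test or threshold and does not say which outcomes are meant.

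Section 9.6 introduces stratified and interaction analyses in general terms, for outcomes in the plural, and then narrows: "Specifically, we will test the difference in sleep quality VAS score change between sexes and those who reported moderate-to-severe insomnia disorder on the ISI" (above 14 versus 14 or below). The method is "including 2-way product terms between the exposure and covariate of interest in linear mixed modeling". The paragraph closes with a rule in general wording: "A significant interaction will be defined by an interaction coefficient with a p-value < 0.05".

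For adjusted models, section 9.6 includes age and sex a priori and adds that "Directed acyclic graphs will be employed to select other potential confounding variables".

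Section 3.2 requires for entry "Insomnia Severity Index (ISI) score of \geq 15 at screening".

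Sections 9.1 to 9.7 contain no multiplicity adjustment, no statement that any subgroup result is exploratory, and no power statement for subgroups.

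**The concern.** An open-ended subgroup list combined with a fixed nominal threshold lets chance produce results that the plan itself would call significant. The list includes variables with little obvious bearing on response, such as phone operating system and tracker. A reader of the final report could not tell which of many interaction tests was planned as a formal test. Section 2.2 expects the study's findings to feed into product improvement and possibly clinical recommendations. That sentence does not mention subgroups, but nothing in the plan keeps subgroup findings out of such use.

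Two related defects sit in the same text. The ISI contrast named in section 9.6 splits at a value that the entry criterion has already used. And sections 9.4 and 9.6 describe the covariates in the multivariable models differently.

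**Working it through.** **Inputs from the documents.** Covariates listed in 9.4: 9, or 10 with alcohol and cannabis separate. Named interactions in 9.6: 2, on sleep quality VAS. Threshold: 0.05 per interaction coefficient. Primary and secondary outcomes in 1.0: 1 + 3 = 4. From 9.1: SD 2, correlation 0.50, difference 1, N = 47, two-sided alpha 0.05, Wilcoxon signed-rank test.

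**Assumptions not in the documents.** All interaction nulls true; one test per covariate; independent covariates; outcome correlation between 0 and 0.7; subgroup splits as shown.

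**1. The plan's own figure.** SD of the paired difference = √(2 × 2² × (1 − 0.50)) = 2, so the standardised effect is 1/2 = 0.5. A noncentral-t calculation with n scaled by 3/π for the Wilcoxon test gives 90.6% power at N = 47; 20,000 simulated Wilcoxon tests give 90.8%. The stated power of at least 90% reproduces. It concerns the overall within-person change only.

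**2. Chance of at least one false positive, independent tests:** 1 − 0.95^m.

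| Tests (m) | Reading | Chance |
|---|---|---|
| 2 | the two named interactions | 9.75% |
| 9 | covariates as listed, one outcome | 37.0% |
| 10 | alcohol and cannabis separate, one outcome | 40.1% |
| 13 | – | 48.7% |
| 14 | first count above even odds | 51.2% |
| 40 | 10 covariates × 4 outcomes | 87.1% |

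With 40 tests the expected number of false positives is 40 × 0.05 = 2.

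**3. Correlated outcomes.** Four outcomes measured in the same people will not be independent. A simulation used 47 participants, ten independent binary covariates with 40% prevalence, no true interactions and 4,000 replicates. It gave 84.8%, 82.3% and 75.6% at outcome correlations of 0.3, 0.5 and 0.7. With the independent case this gives about 75–87%. With nine covariates the simulated values are 81.2%, 78.1% and 71.3%, and 36 independent tests give 84.2%.

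**4. Power for a subgroup difference.** Take the SD of change as 2 (step 1). For a 23/24 split, the standard error of the difference is 2 × √(1/23 + 1/24) = 0.584. A true 1-point difference is then 1/0.584 = 1.71 standard errors. The two-sample t-test with 45 degrees of freedom has 38.9% power (40.3% by normal approximation). For 80% power the difference must be 1.67 points, or 2.04 with a 10/37 split. Both exceed the 1-point overall change that the trial was sized to detect. By normal approximation, 12/35 and 9/38 splits give 32% and 27% power for 1 point. These figures are illustrative: the plan specifies product terms in a mixed model and gives no splits.

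**5. The ISI subgroup.** Entry needs a screening ISI of at least 15. ISI totals are whole numbers, so every participant is above 14 at screening and the comparison group is empty. It could be filled only from a later ISI, such as Day 1. Section 9.6 does not say which measurement defines the groups.

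**The case against.** The strongest objection concerns the reading. Section 9.4 speaks only of examining differences and sets no threshold. The p < 0.05 definition is in section 9.6, directly after two interactions on sleep quality VAS. One fair reading is therefore two formal tests on one outcome, at 9.75%, with descriptive summaries elsewhere. This stands in part: the documents do not say that every covariate will be judged at 0.05. But the rule is worded generally, its paragraph opens generally, and the documents offer no other criterion for the section 9.4 analyses. The wider reading is natural and the plan leaves the matter unsettled.

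A reader might infer three stronger things that the documents do not support.

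- That a false subgroup finding is likely on any reading. On the primary outcome with one test per listed covariate the chance is 37–40%, below even odds. It passes 50% only from 14 tests, for example if subgroups are repeated over outcomes or multi-level covariates are tested coefficient by coefficient. The plan neither states nor rules out either.
- That 47 participants cause the false positives. A valid test keeps its 5% error at any sample size. The small sample lowers power, which makes a significant subgroup less credible; that is a separate point.
- That sections 9.4 and 9.6 flatly contradict each other on covariates. Section 9.4 can be read as the candidate pool and section 9.6 as the selection rule. This is an ambiguity worth one sentence of clarification.

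Low subgroup power is also ordinary when N was set for an overall effect. It argues for caution in wording, not for a larger trial.

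**Conclusion.** The concern holds in conditional form. The plan combines an unlimited subgroup list with one unadjusted significance rule, and neither controls multiplicity nor labels anything exploratory. If the rule covers the section 9.4 subgroups, the false-positive risk is about 37–40% on the primary outcome and about 75–87% for ten covariates over four outcomes. If it covers only the two named tests, the risk is 9.75%. These figures rest on the assumptions listed with the calculation, chiefly true nulls, independent covariates and one test per covariate. Power for a 1-point subgroup difference is at best about 39% under the t-test with an even split and SD of change 2.

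The ISI contrast as written cannot be made on screening values, whichever reading applies. The primary within-person comparison and its sample size are untouched. The text should be amended because subgroup claims made under it could not be properly interpreted.

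**What to change.** In section 9.6:

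- Restrict the p < 0.05 interaction rule to two tests on sleep quality VAS: sex and baseline ISI.
- Enter ISI as a continuous variable and state which ISI assessment is meant. This removes the dependence on an empty group.
- Label the two tests as unadjusted for multiplicity, since together they still carry a 9.75% chance of a false positive.

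In section 9.4:

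- State that all other subgroups are exploratory and will be reported as estimates with 95% confidence intervals, without significance wording.
- State that covariates enter the adjusted models by the section 9.6 rule: age, sex and confounders selected by causal diagrams.

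The cost is SAP wording. No data collection, sample size or primary analysis changes. The downside is that the sponsor can no longer call an incidental subgroup difference significant.

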9.5 Missing Data

Missing data will be imputed with a value of “999”. The proportion of missingness will be evaluated among all covariates and outcome variables. If data are missing on a variable in under 5% of cases and the assumption of missing completely at random can reasonably be made, only observed data will be used in the analysis. If a variable is missing within a range of 5%-40% of cases, use of multiple imputation will be evaluated. Regression analyses will be conducted using only complete cases.

9.6 Statistical Analysis Plan

The primary objective of this study is to determine the impact of Sip2Sleep® use on symptoms of sleep disturbance, as measured by the change in sleep quality VAS scores from 47 participants. Univariate statistics will be generated to describe the distribution of patient characteristics and outcome data. Continuous variables will be described using means, standard deviations, minimums and maximums while categorical variables will be described using counts and percentages. Sleep quality VAS scores will be compared from baseline pre-treatment; and at end of study (post-treatment) of the same individuals. We will enroll up to 80 participants to achieve at least 90% power to detect a mean change in sleep quality VAS scores of 1 points (SD=2) from baseline with a type I error of 0.05 (two-sided) assuming a paired means, dependent Wilcoxon Signed-Rank test. We are testing the null hypothesis that there is no difference between pre-treatment and post-treatment mean sleep quality VAS scores within study participants. Summary statistics will be generated, and paired differences between pre-treatment and post-treatment sleep quality VAS scores will be reported, along with 95% confidence intervals.

Additionally, parametric linear mixed models will be employed to simultaneously account for correlated observations and adjust for confounding variables (Proc Mixed, SAS). Several covariance structures, including compound symmetry and unstructured, will be evaluated by comparing AIC and BIC to identify optimal model fit. Random slope and intercept will also be considered in a similar manner. Patient characteristics (i.e. age and sex) will be included in adjusted models a priori for confounding control. Directed acyclic graphs will be employed to select other potential confounding variables and identify biases during the model fitting process. Large differences will be further examined and may help identify where further calibration of estimation models are needed.

Stratified and interaction analyses will be employed to detect between-subgroup differences in outcomes. Specifically, we will test the difference in sleep quality VAS score change between sexes and those who reported moderate-to-severe insomnia disorder on the ISI (i.e. ISI score > 14) and those who did not (i.e. ISI score ≤ 14). Testing of these differences will be conducted by including 2-way product terms between the exposure and covariate of interest in linear mixed modeling. A significant interaction will be defined by an interaction coefficient with a p-value < 0.05.

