1.0 OBJECTIVES AND ENDPOINTS

Objectives	Endpoints/ Measurements
Primary Objective	

 To observe the effect of the Sip2Sleep® product on sleep quality for participants with self-reported sleep disturbance 	
 Change in average sleep quality score by 1 point as measured by daily 10-point visual analogue rating scale (VAS) from baseline and 1 week of no product use
Secondary Objectives	

 To assess the effect of Sip2Sleep® product on symptoms of sleep disturbance To assess the effect of Sip2Sleep® product on anxiety To assess the effect of Sip2Sleep® product on the level of alertness during the daytime 	
 Change in Insomnia Sleep Index (ISI) by 4.5 points from baseline and 1 week of no product use Change in Generalized Anxiety Disorder-7 (GAD-7) by 4.5 points from baseline and 1 week of no product use Change in average level of alertness during the daytime score by 1 point as measured by daily 10-point visual analogue rating scale (VAS) from baseline and 1 week of no product use
Exploratory Objectives	

 To observe the change in sleep duration via personal health tracking wearable device To observe the change in sleep latency via personal health 	
 Change in average nightly sleep duration as measured via personal health tracking wearable device from baseline and 1 week of no product use Change in average nightly sleep

tracking wearable device
 
3. To identify improvements for future participant-centered study designs using feedback
	
latency as measured via personal health tracking wearable device from baseline and 1 week of no product use
 
3. Assessment of patient satisfaction survey of study experience including design and use of app-based data collection tools

---	--

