6.0 STUDY PROCEDURES

6.1 Study Overview

[figure not shown]

Figure 1. Study Design

Upon enrollment, the study assessments can be accessed via CHLOE mobile app available on Apple iOS and Android devices as well as any web browser. The participant's activities are as follows:

Screening (Day -7 to Day -1):

- Informed Consent
- Complete demographic and medical history data intake.
- Screening Insomnia Severity Index (ISI) assessment.
- Provide preferred shipment address for product shipment during Baseline.

Baseline Period (Day 1 to Day 7):

- Complete Insomnia Severity Index and Generalized Anxiety Disorder-7 (Day 1 only).
- Begin discontinuation of non-prescription products used for sleep.
- Begin nightly use of personal health tracking wearable device through Day 28.
- Complete daily survey to review objective data (sleep duration and sleep latency) from wearable device collection and answer questions about their prior night's sleep quality and level of alertness since waking.
- Receive shipment of study product and instructions for use.

Product Use Period (Day 8 to Day 14):

- Complete Insomnia Severity Index and Generalized Anxiety Disorder-7 (Day 8 only).
- Continue nightly use of personal health tracking wearable device through Day 28.
- Complete daily surveys to review objective data (sleep duration and sleep latency) from wearable device collection and answer questions about their prior night's sleep quality and level of alertness since waking.
- Administer nightly dose of study product 30-60 minutes prior to lying down in bed through Day 14.

No Product Use Period (Day 15 to Day 21):

- Complete Insomnia Severity Index and Generalized Anxiety Disorder-7 (Day 15 only).
- Continue nightly use of personal health tracking wearable device through Day 28.
- Complete daily surveys to review objective data (sleep duration and sleep latency) from wearable device collection and answer questions about their prior night's sleep quality and level of alertness since waking.

Product Use Period (Day 22 to Day 28):

- Complete Insomnia Severity Index and Generalized Anxiety Disorder-7 (Day 22 only).
- Continue nightly use of personal health tracking wearable device through Day 28.
- Complete daily surveys to review objective data (sleep duration and sleep latency) from wearable device collection and answer questions about their prior night's sleep quality and level of alertness since waking.

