- Administer nightly dose of study product 30-60 minutes prior to lying down in bed through Day 28.

End of Study (Day 29):

- Complete Insomnia Severity Index and Generalized Anxiety Disorder-7.
- Complete surveys to review objective data (sleep duration and sleep latency) from wearable device collection and answer questions about their prior night's sleep quality and level of alertness since waking.
- Complete Experience Survey.

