9.1 Sample Size Estimation and Justification

We anticipate needing to screen approximately 200 individuals to enroll up to 80 individuals and achieve a final sample size of approximately 47 evaluable participants. For our primary outcome (i.e. change in average sleep quality VAS scores), we assume a common standard deviation = 2 and a conservative 0.50 correlation between VAS scores. We will have at least 90% power to detect a mean VAS score difference of 1 with $\alpha = 0.05$ using a two-sided Wilcoxon signed-rank test for the difference between dependent means with a final sample of 47 participants. Previous research on participants with insomnia and depression have suggested that single item sleep quality score can effectively detect meaningful changes in sleep quality over time relative to lengthier questionnaires.¹⁶

The secondary objectives include evaluating changes in the ISI, GAD-7 and daytime alertness VAS score. As above, we anticipate at least 90% power to detect a 4.5-point change in the ISI and GAD-7 with an expected standard deviation of 5. For daytime alertness, we anticipate at least 90% power to detect a 1-point change with an expected standard deviation of 2.

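### The primary endpoint in Section 1.0 is referred to baseline and the no-product week, but Sections 9.1 and 9.6 size and test only baseline versus end of study, and no section says which daily ratings enter each average.

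*Combined protocol and SAP*

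**What the plan says.** - **Section 1.0.** The primary endpoint is a change in the average of daily ratings on a "visual analogue rating scale (VAS) from baseline and 1 week of no product use". The three secondary endpoints and the two wearable-device endpoints carry the same double reference.
- **Section 9.1.** Power of at least 90% for a mean difference of 1 (SD 2, correlation 0.50, alpha 0.05), using a "two-sided Wilcoxon signed-rank test for the difference between dependent means with a final sample of 47 participants".
- **Section 9.6.** The comparison is: "Sleep quality VAS scores will be compared from baseline pre-treatment; and at end of study (post-treatment) of the same individuals". The null hypothesis is "no difference between pre-treatment and post-treatment mean sleep quality VAS scores within study participants". Mixed models are planned in addition. The interaction tests refer to an exposure that is not defined.
- **Section 9.3.** A participant is evaluable only with at least 60% of daily assessments both on and off product.
- **Section 6.1.** The sequence is baseline (Days 1-7), product (8-14), no product (15-21), product (22-28), with end of study on Day 29. Among the baseline-week tasks is "Begin discontinuation of non-prescription products used for sleep". Section 3.2 requires "Willingness to do a minimum of 1 week wash out of current OTC or other products for sleep". Product is taken before bed, and in each survey participants "answer questions about their prior night's sleep quality and level of alertness since waking".

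**The concern.** Section 1.0 can be read as two separate references or as one pooled off-product reference. Under either reading the no-product week belongs to the endpoint, and Section 9.6 implements neither. Two statisticians could run different primary tests and each cite the document.

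This matters because there is one sequence and no control group, so Week 3 is the only off-product check after baseline. The remaining reference, Week 1, is when other sleep products start to be withdrawn, so the washout of at least a week overlaps the baseline measurement. Losing those products could depress that week for a time; residual benefit early in the week could raise it. The primary test would put either shift into the product effect. Week 3 could reveal such a shift, but it does not enter the primary conclusion.

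The second gap is the averaging rule. The Day 8 and Day 22 surveys rate product-free nights, and the Day 15 survey rates a product night. If weeks are cut by survey day, each product week contains one product-free night and the no-product week contains one product night.

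**Working it through.** **Inputs from Section 9.1.** SD 2, correlation 0.50, difference 1, two-sided 0.05, Wilcoxon signed-rank test, n = 47. **Assumed.** The same correlation between every pair of weeks, normally distributed weekly means, and all shift and carry-over sizes.

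**1. The plan's own figure.** SD of a paired difference = √(2 × 2² × (1 − 0.50)) = 2.0, so the standardised effect is 1/2 = 0.5. A paired t-test needs 44 for 90% power. Scaling by the Wilcoxon efficiency 3/π gives 44/(3/π) = 46.1, so 47; power is 90.6% at 47 and 89.95% at 46. The 47 reproduces for exactly one paired comparison.

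**2. SD of each candidate contrast.** With equal correlation, SD = √(2² × 0.5 × Σc²), where c are the week weights.

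| Contrast | Σc² | SD |
|---|---|---|
| Week 4 − Week 1 (planned) | 2 | 2.00 |
| Mean of Weeks 2, 4 − Week 3 | 1.5 | 1.73 |
| Mean of Weeks 2, 4 − mean of Weeks 1, 3 | 1 | 1.41 |

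**3. No product effect, baseline week transiently lowered** (40,000 simulated trials per row; % significant).

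| Whole-sample dip | Week 4 − Week 1 | Product weeks − Week 3 | Pooled on − off |
|---|---|---|---|
| 0 | 5 | 5 | 5 |
| 0.1 | 6 | 5 | 6 |
| 0.2 | 10 | 5 | 7 |
| 0.3 | 16 | 5 | 11 |
| 0.5 | 37 | 5 | 21 |

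The pooled contrast keeps half the shift, because Week 1 is half of its reference.

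**4. True 1-point effect, baseline week raised.** At 0.15, 0.3 and 0.5 points, power of the planned test falls from just over 90% to about 79%, 63% and 37%.

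**5. Survey-day windows.** A 1-point effect on every product night gives weekly means of 0, 6/7, 1/7 and 6/7. Week 4 − Week 1 becomes 6/7 = 0.857, standardised 0.43, and power is about 80%.

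**The case against.** The best reply is that the study is observational, that the shifts above are invented, and that Week 3 is used elsewhere. Much of this is fair.

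- The documents give neither the size nor the direction of any baseline shift. Only users of non-prescription sleep products can have a withdrawal effect, and their share is not stated. A loss lasting through all weeks would cancel. At whole-sample dips of 0.1 to 0.2 the inflation is small.
- Week 3 counts for evaluability and may enter the mixed models, where product use is the natural meaning of exposure. The gap concerns the primary test only.
- A reader might infer that the study periods are undefined. They are not: Section 6.1 gives day ranges. What is missing is the assignment of ratings to the two averages.
- A reader might infer that the primary test rests on the single Day 29 rating, because that day is labelled end of study. Sections 1.0 and 9.1 both speak of average scores, which counts against it. The phrase needs tidying, and no power loss should be built on that reading.
- A reader might infer that a confirmatory Week 3 test is obligatory. The documents require only that endpoint and test agree; a pre/post study is permissible if described as one.

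None of this removes the mismatch. An observational study that states a null, an alpha and a power still has to test the endpoint it defines.

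**Conclusion.** The point stands and should be settled before data are analysed. As written, the primary test does not evaluate the primary endpoint of Section 1.0, and the averages it compares are not tied to particular ratings. Both follow from the text alone.

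The consequences are conditional. The false-positive rates of 6% to 37% rest on assumed transient dips of 0.1 to 0.5 points and equal correlation between weeks; the documents support no particular value. The fall to about 80% power needs no shift, only survey-day windows and the plan's own 1-point effect applied to each product night. The sample size of 47 is not an arithmetic error: it is correct for one paired difference, but it was not derived for an endpoint with two references.

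**What to change.** **1. Name one primary contrast** and make Sections 1.0, 9.1, 9.3 and 9.6 agree on it. Carry the choice to the secondary and exploratory endpoints with the same wording. Either:

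- (a) test against the no-product week as Section 1.0 states, saying whether the references are separate or pooled, with the decision rule and its power; or
- (b) keep the pre/post test, remove the no-product reference from Section 1.0, and limit the conclusion to an uncontrolled change from baseline.

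One optional rule under (a) requires the mean of the product weeks to beat both the Week 3 mean and the baseline-week mean, each at two-sided 0.05. No alpha split is needed because both must succeed. Joint power at n = 47 for a 1-point effect, with night-aligned windows:

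| Condition | Joint power |
|---|---|
| Equal effects in both product weeks, no carry-over | about 93% |
| 25% carry-over into Week 3 | about 79% |
| 50% carry-over into Week 3 | about 46% |
| Week 2 shows half the effect | about 68% (about 84% using Week 4 alone) |

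The rule does not protect if both reference weeks are depressed: about 27% false positives at an assumed 0.5-point dip in each. A pooled on/off contrast has power over 99%, or about 93% with 50% carry-over, but keeps half of any baseline shift.

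**2. Assign each rating to the night it describes:** surveys of Days 2-8 (baseline), 9-15 (product), 16-22 (no product) and 23-29 (product). State that the post-treatment value is a weekly average, and apply the 60% completion rule to these windows.

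**3. Define exposure in the supportive mixed model** as on or off product.

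**Cost.** Wording changes, and under (a) a stated power that depends on carry-over. Every rating needed, including Day 29, is already collected.
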